1. STUDY PROTOCOL

1.1 Objectives

This study was designed to demonstrate the safety and effectiveness of the Sonu System for the treatment of patients with moderate to severe nasal congestion.

1.2 Study Design

This is a multi-center, randomized, double blind study of approximately 50 subjects suffering from moderate to severe nasal congestion. Three sites will participate in enrollment. Those who meet the inclusion/exclusion criteria will be invited to participate in the study.

After signing an Informed Consent Form and providing Demographic Information, Medical History, Allergy History, and Medications, the subject will receive the Sonu Device (device and smartphone [if needed] and the app). Subjects will complete the Total Nasal Symptom Score (TNSS) questionnaire, Visual Analog Scale (VAS) for Headache or Facial Pain, SNOT-22 and PROMIS Sleep Disturbance Questionnaire within the App.

Subjects will be randomized to either receive treatment for two weeks, or sham therapy for two weeks. Interventional treatment arm consists of using Sonu Acoustic Resonance Therapy (ART) for 15 minutes, twice a day. Sham consists of using non-resonant acoustic energy (2 kHz, 2 seconds duration tone every 10 seconds at 50% of therapeutic volume) for 15 minutes, twice a day.

Treatment (or sham) will be completed twice daily, during a morning window from 5am to 12pm and during an evening window from 5pm to 12am. Treatments will automatically stop at 15 minutes. Subjects will complete the TNSS questionnaire and the VAS-HA/FP immediately after the second treatment each day. After the second treatment on the 7th and 14th days subjects will also complete the SNOT-22 and PROMIS questionnaire.

The Total Nasal Symptom Score (TNSS; possible score of 0-12) is a validated patient-reported outcome measure for nasal quality of life research. The TNSS is the sum of 4 symptom subdomains for rhinorrhea, nasal congestion, nasal itching, and sneezing, each self-rated by the subject using a scale of 0=None, 1=Mild, 2=Moderate, or 3=Severe. Subjects will complete the TNSS reflecting on the previous 24 hours at baseline and after the second treatment (treatment or sham), every day over the 2 week period.

The Visual Analog Scale for Headache and/or Facial Pain (VAS-HA/FP) is a measure comprised of a line where patients mark the severity of any headache or facial pain they experience, measured in a range from 0 - 100. Subjects will complete the VAS-HA/FP at baseline and after the second treatment (treatment or sham), every day over the 2 week period.

The SNOT-22 is a validated patient-reported outcome measure for quality-of-life research, comprised of 22 questions with possible answers ranging from 0 - 5. The SNOT-22 will be collected at baseline, after week 1 of therapy or sham, and after week 2 of therapy or sham. All results will be recorded via the App.

The PROMIS Sleep Disturbance Scale is a measure that assesses the pure domain of sleep disturbance in adults 18 years and older. It consists of 8 questions with possible

answers ranging from 1 - 5. This scale will be completed at baseline, after week 1 of therapy or sham, and after week 2 of therapy or sham. All results will be recorded via the App.

At the end of the two weeks participants will be asked one question regarding their thought about which arm of the study they were randomized to.

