1.2 Study Endpoints

Safety and efficacy were evaluated by the following endpoints. Primary Endpoints.

- Primary Safety as defined as a lack of serious adverse events (SAEs).
- Primary effectiveness as defined by a statistically significant improvement in nasal congestion sub-score of TNSS, comparing baseline congestion at screening versus daily congestion averaged over 2 weeks (Sonu vs. Sham).

Secondary Endpoints

- Secondary Safety as defined as a lack of adverse events (AEs).
- Secondary effectiveness as defined by a statistically significant improvement in 24hour reflective TNSS comparing baseline TNSS at screening versus daily TNSS averaged over 2 weeks (Sonu vs. Sham).

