2. STATISTICAL PLAN

The study will implement the intention-to-treat (ITT) principle, or, "analyze as randomized", which is recognized as an important protection against bias, namely balancing both known and unknown factors and eliminating selection bias. We will first compare the study subjects demographic and clinical factors to ensure the comparability between two treatment groups. For categorical variables, counts and percentages will be calculated and chi-square test or Fisher's exact test will be performed. For continuous variables, Shapiro-Wilk normality test will be performed, and either t-test or Wilcoxon rank test will be performed where appropriate. Changes in symptom scores and nasal congestion from baseline to follow-up visits will be evaluated using a paired t-test or signed rank test. Multilevel linear mixed models will be built to examine the association between treatment and outcomes. We chose this method because it handles unbalanced data and produces less biased significance than other analysis techniques- due to making use of all available data and incorporating the correlation between time points. Because there are only two time points, an unstructured correlation structure is used. The design effects include main effects of treatment group, time and the group by time interaction, while controlling for study subjects' demographic and clinical factors. We will also examine the different effect between allergic vs non-allergic rhinitis by including it as a covariate and its interaction with treatment in the models. All the analyses use a two-sided test and p<0.05 is considered to be statistically significant.

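### The daily diary is scheduled only after the second session, and nothing provides for a score on days without one, so the 2-week average can come to rest on session days alone

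*Combined protocol and SAP*

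**What the plan says.** The section 1.2 headed Study Design asks for two sessions a day, "during a morning window from 5am to 12pm and during an evening window from 5pm to 12am". It ties the diary to the second of them: "Subjects will complete the TNSS questionnaire and the VAS-HA/FP immediately after the second treatment each day". A later paragraph of that section repeats the link for the TNSS: "Subjects will complete the TNSS reflecting on the previous 24 hours at baseline" and then "after the second treatment (treatment or sham), every day over the 2 week period". SNOT-22 and the PROMIS sleep scale are likewise placed after the second session on days 7 and 14.

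The section 1.2 headed Study Endpoints builds the primary effectiveness endpoint on these diary scores, "comparing baseline congestion at screening versus daily congestion averaged over 2 weeks (Sonu vs. Sham"), and the secondary endpoint in the same way, "comparing baseline TNSS at screening versus daily TNSS averaged over 2 weeks (Sonu vs. Sham").

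Section 2 (Statistical Plan) states: "The study will implement the intention-to-treat (ITT) principle". It explains this as analysing subjects as they were randomised, in order to protect against bias. It plans a mixed model on all available data and says the model has two time points.

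The documents do not say what happens to the questionnaire when a session is missed or when device use stops. They do not say whether the app opens the diary only after a session. They give no minimum number of diary days and no rule for missing days.

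**The concern.** The diary has one stated trigger, and that trigger is an act of adherence. If sites and the app follow the text literally, an evening without a session gives no score, and a subject who abandons the device gives none from then on. Whether an outcome is observed then depends on behaviour after randomisation. That behaviour may depend on how the subject feels and may differ between arms.

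The primary endpoint is exposed directly, because it is a mean of these scores. The secondary TNSS endpoint and the VAS share the exposure. SNOT-22 and PROMIS are collected only twice after baseline, so a single missed session on day 7 or 14 could cost a whole assessment. Scores that were never collected cannot be recovered at analysis.

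**Working it through.** **Step 1. The text.** Every sentence that schedules the daily scores places them after the second session. Read strictly, a missed morning session also matters: the evening session is then the first of that day, and it is unclear whether a second treatment, and hence a diary entry, occurs.

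**Step 2. Does the analysis repair it?** The plan's model has two time points, although up to 14 daily scores are intended. The natural inference is that the daily scores are averaged before modelling. Unscored days then drop out within each subject, and a mixed model on the averages cannot see that they are missing. A model of the daily scores would use more of the data, but it would not correct missingness driven by symptoms that were never recorded.

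**Step 3. Size when there is a true effect.** The documents give no adherence, effect size or SD, so there is no stated figure to reproduce and every input below is assumed. Let m be the share of evenings with no session and no score, d_on the arm difference on session days, and d_off the arm difference on the other days.

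- All-day effect = (1 − m) × d_on + m × d_off
- The scored-day average estimates d_on, so the overstatement is m × (d_on − d_off)
- With no carry-over (d_off = 0), the relative overstatement is 1/(1 − m) − 1, that is, 1/adherence − 1

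For d_on = 0.6 congestion points:

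| m | All-day effect, no carry-over | Relative overstatement | All-day effect, half carry-over | All-day effect, full carry-over |
|---|---|---|---|---|
| 10% | 0.9 × 0.6 = 0.54 | 1/0.9 − 1 = 11% | 0.57 | 0.60 |
| 20% | 0.8 × 0.6 = 0.48 | 1/0.8 − 1 = 25% | 0.54 | 0.60 |
| 30% | 0.7 × 0.6 = 0.42 | 1/0.7 − 1 = 43% | 0.51 | 0.60 |

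The overstatement therefore runs from 0 (full carry-over) to 0.18 points (0.60 − 0.42: 30% missed, no carry-over).

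**Step 4. Size when there is no true effect.** Let skipped days differ from session days by g points, and let both arms have the same all-day mean μ. If s is the session-day mean, then μ = s + m × g, so s = μ − m × g. The spurious arm difference is (m_active − m_sham) × g in absolute size.

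- 10% against 10% skipped: 0
- 20% against 10%, g = 0.5 to 1.0: 0.10 × 0.5 to 0.10 × 1.0 = 0.05 to 0.10
- 30% against 10%, g = 0.5 to 1.0: 0.20 × 0.5 to 0.20 × 1.0 = 0.10 to 0.20

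The direction is not determined. It depends on which arm skips more and on whether skipped days are worse or better.

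**Step 5. What that could do to the test.** Assume 25 per arm (about 50 subjects, 1:1), an SD of 0.6 and a two-sided 0.05 normal test. SE = 0.6 × √(2/25) = 0.170. A bias of 0.10 to 0.20 is 0.59 to 1.18 SE, and the rejection rate under no effect rises from 5% to 9.1% to 21.8%. With an SD of 0.7, SE = 0.198, the shift is 0.51 to 1.01 SE, and the rate is about 8% to 17%. With 20% against 10% skipped and g = 0.5 (bias 0.05, SD 0.6), it is about 6%. With equal skipping it stays at 5%.

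**The case against.** Much of the other side's case stands.

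- **The text also asks for a score every day.** No app lock-out is described, and the reference to the second session may only mark the time of day for a subject on schedule. A reader might infer that the endpoint certainly averages treated days only. The documents do not support that; it is a conditional risk. What remains is that no step secures a score when there is no session.
- **Intention-to-treat is not contradicted.** A reader might infer that the plan breaks its own principle. Section 2 explains the principle as analysis by randomised arm, and missing diary days move nobody between arms. The principle's purpose of protecting against bias can be weakened, and a subject without any post-baseline score cannot contribute one.
- **"On-treatment average" is not an exact description.** A day with a morning session and a skipped evening is treated but unscored. A day with only an evening session may be scored although only partly treated.
- **The 24-hour recall softens isolated gaps.** A score missed one evening would mostly have described the period after the previous evening's session. Much of any loss from the skipped session falls in the next evening's look-back, which is recorded if that session is done. This does not help with runs of missed days or with stopping.
- **The magnitudes are chosen, not estimated.** The 11% to 43% figures assume no carry-over. The 9% to 22% false-positive range assumes strongly unequal skipping, a sizeable symptom difference and an SD that the documents do not give. They illustrate a mechanism and do not describe this trial's error rate.

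**Conclusion.** The concern holds as a gap in data collection with a conditional consequence. The daily scores have a single stated trigger, and nothing covers days without a second session or the time after device use stops. If the diary is not completed then, the congestion and TNSS averages rest on session days and the as-randomised comparison is weakened. It is biased if skipping depends on symptoms and differs by arm.

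The documents cannot fix the size, and the range includes zero: full carry-over removes the overstatement, and equal skipping with no true effect creates no spurious difference. The assumed adverse cases are best read as an upper end: 0.10 to 0.20 points on the 0-3 scale, or an overstatement of up to 1/adherence − 1. The change is worth making because it costs little, concerns the primary endpoint of a trial of about 50 subjects, and cannot be made after the data are in.

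**What to change.** Separate the score from the session.

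- The app asks every randomised subject for the TNSS and VAS each evening through day 14, and for SNOT-22 and PROMIS on days 7 and 14.
- The prompt follows the second session if it is done. Otherwise it appears at a set time near the end of the evening window.
- Prompting continues through day 14 for subjects who stop using the device.
- The app logs whether each session was done.
- The primary average includes all scored days, with or without a session.

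A prompt does not guarantee an answer, so the plan should also state which effect is being estimated, the minimum number of diary days and the handling of missing days, with a sensitivity analysis.

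**Cost.** A few protocol sentences and a change to the app's prompting, probably small because the app already collects these scores, although the documents do not describe how it prompts. Scores on days without a session will not be taken just after one; the logged flag documents this. If the effect does not carry over, the all-day difference is also smaller than the session-day difference. With the assumed 0.6-point effect, an SD of 0.7 and 25 per arm, nominal power falls from 86% to 78% at 10% missed evenings and to 68% at 20%. That reflects the as-randomised question and is not a defect of the fix.

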1.2 Study Endpoints

Safety and efficacy were evaluated by the following endpoints. Primary Endpoints.

- Primary Safety as defined as a lack of serious adverse events (SAEs).
- Primary effectiveness as defined by a statistically significant improvement in nasal congestion sub-score of TNSS, comparing baseline congestion at screening versus daily congestion averaged over 2 weeks (Sonu vs. Sham).

Secondary Endpoints

- Secondary Safety as defined as a lack of adverse events (AEs).
- Secondary effectiveness as defined by a statistically significant improvement in 24hour reflective TNSS comparing baseline TNSS at screening versus daily TNSS averaged over 2 weeks (Sonu vs. Sham).

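### Baseline congestion appears to be one 24-hour rating set against a two-week mean, which costs precision in the Sonu-versus-sham contrast; a three-evening pre-treatment diary used as a covariate would recover some of it

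*Combined protocol and SAP*

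**What the plan says.** Section 1.2 Study Endpoints defines primary effectiveness on the TNSS congestion item by "comparing baseline congestion at screening versus daily congestion averaged over 2 weeks (Sonu vs. Sham". The secondary effectiveness endpoint has the same structure for total TNSS.

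Section 1.2 Study Design gives the measurement. Items are "each self-rated by the subject using a scale of 0=None, 1=Mild, 2=Moderate, or 3=Severe". On timing: "Subjects will complete the TNSS reflecting on the previous 24 hours at baseline and after the second treatment", then "every day over the 2 week period". No run-in, baseline diary or averaged baseline is described. That the baseline is a single rating is therefore implied, not stated. The baseline questionnaires are already completed in the app, after the device is handed out.

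The trial enrols "approximately 50 subjects suffering from moderate to severe nasal congestion". The inclusion and exclusion criteria are referred to but not set out in the text available, so any numeric entry threshold is unknown.

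Section 2 (Statistical Plan) describes a mixed model with two time points and effects for group, time and group by time, adjusted for demographic and clinical factors that are not named. Adjustment for baseline congestion is not stated. Paired t-tests or signed rank tests of change from baseline are also planned. On significance: "All the analyses use a two-sided test and p<0.05 is considered to be statistically significant".

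**The concern.** The two sides of the comparison are measured with very different precision. The follow-up side averages up to 14 daily ratings. The baseline side is one rating on a four-level item, covering one 24-hour period. Baseline is one of only two modelled time points, so with complete data the group-by-time term is the difference between arms in change from that rating. Its day-to-day noise goes straight into the primary test.

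Two things are at stake. The first is precision in a trial of about 50 subjects for which no effect size, SD or power is given. The second is how the within-arm results read. If people enter because their screening rating is high, part of the later fall is regression to the mean, and the paired tests will count it as improvement in both arms.

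**Working it through.** **Inputs from the documents.** One baseline rating (k = 1, implied); daily follow-up for two weeks (m = 14); item scored 0-3; about 50 subjects; two-sided 0.05.

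**Assumed, because the documents do not say.** 25 per arm; the share of daily variance that lies between subjects (ICC, written ρ); the serial correlation of daily noise (AR(1), φ); the SD of true individual change; and, in simulations, entry on a screening congestion score of 2 or more.

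**1. The plan's own figure.** The sample size cannot be reproduced, since no effect size, SD or power is given. The detectable difference at 80% power is (1.96 + 0.84) × √(2/25) = 0.79 SD of whatever outcome is analysed, so that SD matters.

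**2. Where the noise sits.** Set the total daily variance to 1 and let daily noise be independent. Then Var(change) = (1 − ρ)(1/k + 1/14). With k = 1 the baseline rating supplies 1/(1 + 1/14) = 93% of the noise and the 14-day mean 7%.

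**3. Idealised gain from three days.** This step assumes no selection, no variation in true response and no serial correlation.
- Change score: (1/3 + 1/14)/(1 + 1/14) = 0.405/1.071 = 0.38, a 62% cut in variance whatever ρ is. At ρ = 0.5 the detectable difference falls from 0.79 × √0.536 = 0.58 to 0.79 × √0.202 = 0.36 daily SDs.
- Baseline as covariate: residual variance = Var(F) − Cov(B,F)²/Var(B), where F is the 14-day mean and B the baseline. At ρ = 0.5, Var(F) = 0.5 + 0.5/14 = 0.536 and Cov = 0.5. With one rating, Var(B) = 1 and the residual is 0.536 − 0.250 = 0.286, already 47% below the change-score variance of 0.536. With three ratings, Var(B) = 0.5 + 0.5/3 = 0.667 and the residual is 0.536 − 0.375 = 0.161, a further 44% cut.
- With serial correlation, the 62% change-score cut shrinks to 31% at φ = 0.5 and 16% at φ = 0.7.

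**4. More realistic simulation.** This adds 0-3 scoring, entry at 2 or more, ICC 0.4-0.8, true-change SD 0.3-0.5 and a three-day diary separate from the entry rating. The table gives the change in variance relative to the single screening rating.

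| Daily noise | Unadjusted change score | Baseline as covariate |
|---|---|---|
| Independent | 15%-37% cut | about 19%-39% cut |
| AR(1), φ 0.5-0.7 | from a 21% cut to a 7% increase | about 4%-25% cut |

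The change score can lose because entry at 2 or more compresses the screening rating to two values, whereas the diary mean is not compressed.

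**5. What that is worth.** A variance cut v shrinks the detectable difference by 1 − √(1 − v) and equates to 50/(1 − v) subjects. For 19%-39% that is 10%-22%, or 62-82 subjects. For 4%-25% it is 2%-13%, or 52-67 subjects.

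**6. Regression to the mean.** With entry at 2 or more and no treatment effect, simulations with ρ 0.3-0.7, φ 0 or 0.5 and true-change SD 0 or 0.4 gave a fall of 0.09-0.39 points from screening to the 14-day mean. Measured from a separate diary, the fall was 0-0.06. In one null scenario (ρ = 0.5, independent noise, true-change SD 0.4) the between-arm difference was about 0.00 with type I error about 5%, while the paired within-arm test was significant in 67% of runs. That scenario had a mean fall of 0.31 and SD 0.61, so with 25 subjects t is about 0.31/(0.61/5) = 2.5. A less selected population gave a fall of 0.16 and SD 0.58, so t is about 0.16/(0.58/5) = 1.4. The inflation depends heavily on the assumed entry rule and population.

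**The case against.** The strongest reply is that nothing is wrong with the primary comparison. The trial is randomised and double blind, and regression to the mean is equal in expectation in both arms. That stands. A reader might infer that a noisy, selected baseline biases Sonu against sham; the documents do not support this, and the null simulation shows no such bias.

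The second reply is that the gain is uncertain, and this also stands. Consecutive 24-hour ratings in people with rhinitis are likely to be correlated. A reader might infer that three diary days would remove most of the baseline noise; that follows only from independent days. With serial correlation, the unadjusted change score may not improve at all.

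Third, adjusting for the existing single rating is cheaper and recovers part of the loss without altering the schedule. True, but the gains in the covariate column above are over and above that adjustment, so the two measures complement each other.

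Fourth, the regression-to-the-mean figures rest on an unseen entry rule. If entry rests on symptom history rather than the screening rating, they largely disappear. Nor does the diary change who is enrolled: subjects who are usually mild but had one bad day would still enter, with little room to improve.

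A mismatch in time of day between baseline and follow-up adds little, since both ratings look back over 24 hours.

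**Conclusion.** The point holds as a loss of precision in a valid comparison. It rests on reading the baseline as one rating, which the text implies, and on the two-time-point group-by-time model, which it states. The size cannot be fixed from the documents. Under the assumptions shown, a three-evening baseline used as a covariate reduces the variance by about 19%-39% with independent daily noise and about 4%-25% with serial correlation of 0.5-0.7. The covariate gain was positive in every setting tried; the change-score gain was not, so the benefit is dependable only if the diary mean enters as a covariate.

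The within-arm paired tests are inflated if entry depends on the screening rating. That affects how supporting results are read, not the primary test. This is a worthwhile low-cost improvement for a small trial, not a flaw that undermines it.

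**What to change.** After consent and device hand-out, have the app collect the same evening TNSS on three consecutive days before the first session, and randomise at the end of those days. Use the mean of those ratings as the baseline for both congestion and total TNSS, entered as a covariate in the analysis of the two-week mean. Keep the screening rating for eligibility, leave the entry criteria unchanged, and report an analysis from the screening rating as a sensitivity analysis. State in advance how a missed diary evening is handled. Describe within-arm changes as descriptive, with a note on regression to the mean.

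The cost is a protocol amendment and an app change, treatment starting three days later, three more short entries per subject, and possibly a few missed entries or dropouts before randomisation. The documents do not say how the arm is assigned or set on the device, so the sponsor must confirm that this can be done after the diary. If the schedule cannot change, adjusting for the existing screening rating is the fallback and recovers part of the loss.
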